5.3.7 Subgroup Analyses

The primary outcome and the secondary outcomes AFSS AF burden (#8 in Section 5.1.4), AFSS symptom score (#9), SF-36 physical (#11), SF-36 mental (#12), ESS sum score (#13), and FOSQ sum score (#14) will be analysed in the following subgroups:

- Male vs females
- Age below median vs. age above median
- Duration of AF below median vs. duration of AF above median
- Left atrium size below median vs. left atrium size above median
- BMI below median vs. BMI above median
- Patients that use the CPAP mask for more than 4 hours a night vs. patients that use the CPAP mask for less than 4 hours a night (no change in the usual care group)
- Patients who either have a DC cardioversion or start treatment of Flecainide, Dronedaron, or Amiodarone after inclusion vs. patients who do not have a DC cardioversion or start treatment of either Flecainide, Dronedaron, or Amiodarone after inclusion.

A comparison of the effect of CPAP between the subgroups will be analysed by adding a subgroup indicator variable and an interaction term between the subgroup and treatment to the linear regression model. A significant subgroup effect will be declared if the interaction term is statistically significant at the 5% level. Within- and between subgroup effects will then be reported with mean differences and 95% confidence intervals.

6 Safety Analyses and Adverse Events

At each follow up visit all serious adverse events will be recorded in the Viedoc database with description of adverse event, with start and end date of the event. Information will be provided on the severity, causality and expectedness of the adverse event

Investigator records the maximum intensity of each AE using the levels mild, moderate, severe or life-threatening. Applicable treatment given and outcome of event will also be recorded

The summary of events will be exported from the Viedoc database. The summary of number of events will be used, rather than number of patients. Safety variables will be tabulated and presented for all patients in the safety set.

STATISTICAL ANALYSIS PLAN for Effect of treatment of sleep apnea in patients with paroxysmal atrial fibrillation.

7 Statistical Software

Stata/SE 16.0 (StataCorp LLC, College Station, TX) will be used to perform the statistical analyses, except for the analyses of the dichotomous outcome, which will be done with Matlab R2014a (The MathWorks, Inc.).

8 References

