2.4 Statistical Framework

2.4.1 Hypothesis Test

This trial is designed to establish the superiority of treatment of CPAP over usual care for the total burden of atrial fibrillation in patients with paroxysmal atrial fibrillation and concomitant moderate-severe sleep apnea.

- The primary null hypothesis is that the change in the total burden of atrial fibrillation from baseline (one month prior to randomization) to the last three months of the intervention period is equal with CPAP treatment and usual care.
- The primary alternative hypothesis is that there is a difference in change in the total burden of atrial fibrillation from baseline (one month prior to randomization) to the last three months of the intervention period between CPAP treatment and usual care.

There is only one identified primary analysis in this trial. All other efficacy analyses will be regarded as supportive or exploratory.

STATISTICAL ANALYSIS PLAN for Effect of treatment of sleep apnea in patients with paroxysmal atrial fibrillation.

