5.2 General Definitions and Derived Variables

5.2.1 Duration of atrial fibrillation

Duration of atrial fibrillation measured in hours and minutes will be converted to % of time in atrial fibrillation.

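### SAP 5.3.7 tests four continuous effect modifiers only as median splits, which costs those exploratory interaction tests about 36% of their information if the CPAP effect changes linearly with a roughly normal modifier

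*SAP*

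**What the plan says.** SAP 5.3.7 names seven subgroup factors. Four of them are continuous measurements entered as two groups. The entry for age is "Age below median vs. age above median". Left atrium size is handled in the same way, as "Left atrium size below median vs. left atrium size above median", and so are duration of AF and BMI.

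Each is tested by "adding a subgroup indicator variable and an interaction term between the subgroup and treatment to the linear regression model", and the decision rule is that "A significant subgroup effect will be declared if the interaction term is statistically significant at the 5% level". The rule covers the primary outcome and six secondary outcomes, so these four factors give 4 × 7 = 28 interaction tests. No fixed cut-points are given, values equal to the median are not assigned to a group, and no analysis in the SAP keeps these modifiers continuous. SAP 2.4.1 sets the status of everything outside the primary analysis: "All other efficacy analyses will be regarded as supportive or exploratory".

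**The concern.** The question behind these tests is whether the CPAP effect varies with age, AF duration, atrial size or body mass. A median split treats patients just either side of the cut as different and patients at the centre and the extreme of the same half as alike. If the effect changes gradually, the interaction test loses power, and the between-subgroup interval says less than the data could. Interaction tests in 100 patients are weak to begin with. The cut also depends on this sample, so a result stated as above or below the median is hard to carry to another population.

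There is also a smaller gap in definition. The SAP does not define duration of AF as a subgroup variable. Its only similarly named entry, in 5.2.1, reads "Duration of atrial fibrillation measured in hours and minutes will be converted to % of time in atrial fibrillation". That is recorder time, the scale of the primary outcome, and no time window is given. The baseline list in SAP 4.3 contains no time since diagnosis.

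**Working it through.** **Inputs.** SAP 2.3 gives mean AF burden 34%, a 25% reduction as the target, SD 12 with an allowance to 15, two-sided 5%, 80% power and 100 patients. SAP 2.1 gives 50 per arm. The target difference is 0.25 × 34 = 8.5 points. The documents give no distribution for the four modifiers and no expected interaction, so both are assumptions here.

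**1. The plan's own sample size.** n per group = 2 × (1.96 + 0.84)² × SD² / 8.5².
- SD 12: 2 × 7.849 × 144 / 72.25 = 31.3, so 32. The noncentral t gives 33, as stated.
- SD 15: 2 × 7.849 × 225 / 72.25 = 48.9, so 49. The noncentral t gives 50, or 100 in total, as stated.

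The figures reproduce. They size the primary comparison only; the documents state no power for any interaction.

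**2. Information kept by a median split.** For an effect that changes linearly with the modifier, the efficiency of the split relative to the continuous term is the squared correlation between the modifier and its split indicator. For a normal modifier this is 2/π = 0.637, so 36% is lost. Other shapes, by simulation:

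| Modifier | Kept | Lost |
|---|---|---|
| Uniform | 75% | 25% |
| Age, normal (assumed mean 60, SD 10), truncated to 18–75 | 66% | 34% |
| Normal | 64% | 36% |
| Lognormal, log-SD 0.5 | 52% | 48% |
| Exponential | 48% | 52% |

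Heavier skew costs more on the raw scale (73% for a lognormal with log-SD 1). But a median split is the same before and after a log transform. If the effect is linear in the log of such a modifier, the normal figure of 36% applies.

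**3. Power at N = 100 for AF burden.** Take an interaction with an expected difference of 8.5 points between halves, as large as the whole target effect.
- Split: four cells of 25, SE = SD × √(4/25) = 0.4 SD.
- Continuous, in SD units of the modifier: SE = 2 SD / √100 = 0.2 SD. The matching slope is 8.5 / (2 × √(2/π)) = 8.5 / 1.596 = 5.33 points per SD.
- SD 15: split 8.5 / 6.0 = 1.417, Φ(1.417 − 1.96) = 29%. Continuous 5.33 / 3.0 = 1.776, Φ(1.776 − 1.96) = 43%.
- SD 12: split 8.5 / 4.8 = 1.771, power 42%. Continuous 5.33 / 2.4 = 2.219, power 60%.

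The squared ratio (1.417 / 1.776)² = 0.64 agrees with step 2.

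**4. Check by simulation.** The SAP's regression (treatment, site, baseline, modifier, product) was run 4,000 times per scenario at SD 15 with a normal modifier. The baseline was simulated with no prognostic value.
- Linear interaction: 28% power with the split, 41% with the continuous term.
- No interaction: rejection about 5% for both.
- Effect stepping at the median by 8.5 points: 28% with the split, 20% with the continuous term.

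**5. A smaller interaction.** At 4.25 points between halves, the formulas of step 3 give 11% (split) against 14% (continuous) at SD 15, and 14% against 20% at SD 12.

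**The case against.** The strongest reply is that little hangs on this. SAP 2.4.1 makes these tests supportive or exploratory, the primary model in 5.3.1 already keeps baseline burden continuous, and false positives do not increase. Median-split subgroups with a formal interaction test are common and easy to read. The continuous test is itself weak: for a plausible interaction of half the target effect, neither version has useful power, and a null result says little. All of this stands. It limits the weight of the point, but it gives no reason to discard information when the better test uses the same model.

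It is also true that the continuous term is worse if the effect really steps at the median, and that a slope in 100 patients can be pulled by a few extreme values. The first needs the step to fall at this sample's median, for which the documents give no reason. The second is a real cost and is met by a transform chosen in advance.

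Three stronger readings are tempting, and the documents do not support them.
- **The trial loses a third of its information, or 100 patients act as 64.** The loss concerns the interaction term only, and its size depends on an assumed distribution and a linear effect.
- **Power falls from 80% to 61%.** The arithmetic is right: Φ(2.80 × 0.798 − 1.96) = 61%. But it starts from a power that these tests do not have in the settings examined here.
- **The AF-duration subgroup conditions on the outcome.** Splitting on follow-up burden would be harmful: in a simulation (4,000 trials, n = 100, effect −8.5, SD 12, correlation 0.5) both within-subgroup effects shrink to about −3.8. But 5.3.7 does not say that follow-up recorder time is used, and 5.2.1 describes a unit conversion, not a subgroup variable. The SAP also uses duration for an AFSS domain. The term is ambiguous; a bias has not been shown.

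**Conclusion.** The point holds as an inexpensive improvement to exploratory analyses. Under a linear change in effect and a roughly normal modifier, each of these interaction tests gives up about 36% of its information. For AF burden, with an interaction as large as 8.5 points between halves, this means 29% power instead of 43% at SD 15, or 42% instead of 60% at SD 12. The loss is about 25% for a uniform modifier and about half for the moderately skewed ones examined, and there is none if the effect steps at the median. The power figures treat SD 12 or 15 as the residual SD; baseline adjustment would raise power under both approaches. The relative loss carries over to the other six outcomes, but the power figures do not, since the SAP gives no SD for them. The continuous test is better but remains underpowered. The undefined duration of AF and the unassigned ties are secondary clarifications.

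**What to change.** In SAP 5.3.7, for age, duration of AF, left atrium size and BMI:

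1. Test the product of treatment and the centred continuous modifier, with the modifier itself, in the same regression. Report the change in CPAP effect per unit (for example per 10 years or per 5 kg/m²) with a 95% CI. Name the measure and unit of left atrium size, which the SAP leaves open.
2. Fix in advance a transform, such as the log, for a modifier expected to be skewed, with AF duration the likeliest. If baseline-month burden is chosen, the transform must allow for zeros.
3. Check linearity with a plot or a pre-specified spline or quadratic term. The median split gives two points and cannot do this.
4. Keep the median split for display only, as at or below the median against above it, so that ties are assigned.
5. State that duration of AF is a pre-randomisation variable, and say which: time since diagnosis or burden in the baseline month.

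The cost is SAP wording and the same number of interaction tests, plus the linearity check. The downside is that the test assumes a linear change in effect on the chosen scale and is more sensitive to extreme values than a split.

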All patients will undergo a sleep screening using a portable polygraph system at home. Nasal airflow, chest and abdominal effort, pulse oximetry and body position are recorded simultaneously. Automated analysis using standard software is used. In addition the analyses will be reviewed and corrected by an independent SDB specialist. Standard definitions will be used for the scoring of sleep disorders; hypopnea defined as a \geq 30% reduction in airflow in combination with a drop in O₂ saturation of \geq 3%, apnea defined as a \geq 90% reduction in airflow for \geq 10 sec and classified as either obstructive (if accompanied by typical thoracic-abdominal breathing effort) or central (if there is no effort). The number of episodes of apnea-hypopnea per hour is referred to as apnea-hypopnea index (AHI). Patients with an index \geq 15/h are included in the present study. Patients with two or more sleep mappings must have an average AHI \geq 15/h to be included. During the sleep mapping oxygen saturation will be recorded.

All sleep recordings will be read in a core lab by persons unaware of treatment allocation.

Tolerability test: We know from previous trials that at least 20% of the population do not tolerate CPAP or ASV treatment for various reasons. In order to reduce the number of drop outs, a simple tolerability test will be performed prior to randomization. The patients will be asked to use an automatic CPAP machine every night for a week. The last night of tolerability test, oxygen saturation will be recorded as well. If mask treatment is tolerated they will be invited to participate. Compliance is defined as > 4 hours per night every night for 7 nights.

Reveal insertable cardiac monitor.

Recordings for occurrence of AF will be performed by an implantable cardiac monitor; Medtronic's Reveal® Insertable Loop Recorder. The device is inserted subcutaneously, continuously records single-lead ECG and has an algorithm designed to detect AF by looking at the irregularity and incoherence of R-R intervals. A previous study has demonstrated the device ability to correctly identify AF in 96.1% of patients and to correctly exclude AF in 97.4% of patients²³

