3.2 Adherence

3.2.1 Adherence to Allocated Treatment

CPAP therapy will be monitored remotely using AirView™ (ResMed) and in addition data will be downloaded from the device SD card every three months. The data will be downloaded in the ResScan software program for compliance calculations.

Adherence to the intervention will be presented as mean (\pm SD) duration of adherence to CPAP therapy in the last three months of treatment before ablation procedure (period of primary endpoint). The residual apnea-hypopnea index during CPAP use, as measured by the CPAP device will also be presented as average events per hour.

The number and % of participants using the CPAP device more than four hours per night will be presented.

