4.3 Baseline Patient Characteristics

The following patient demographics and baseline characteristics will be summarised:

Age, years

Gender, no. (%)

BMI, kg/m²

Neck circumference, cm

Waist-to-hip ratio

LVEF, %

AHI, per hour

Obstructive apnea index, per hour

Central apnea index, per hour

Minimum SpO₂, %

SpO₂ time < 90%, %

Epworth Sleepiness score

FOSQ score

STATISTICAL ANALYSIS PLAN for Effect of treatment of sleep apnea in patients with paroxysmal atrial fibrillation.

SF-36 (Physical and Mental Component Summary)

Cardiovascular disease, no. (%)

Hypertension no. (%)

Diabetes mellitus no. (%)

Stroke/TIA no. (%)

COPD/asthma no. (%)

Previous DC cardioversion no. (%)

Beta-blocker no. (%)

ACE-I + ARB no. (%)

Calcium channel blocker no. (%)

Diuretic no. (%)

Statin no. (%)

NOACs no. (%)

Antidiabetic medication no. (%)

Flecainide no. (%)

Dronedarone no. (%)

Hb, g/dl

Creatinine, mcmol/l

NT-proBNP, ng/L

Troponin T, ng/L

Patient demographics and baseline characteristics will be summarised by randomised treatment arm and overall using descriptive statistics (N, mean, standard deviation, median, 25/75 percentiles for continuous variables, and number and percentages of patients for categorical variables. There will be no statistical analysis of treatment difference. Any clinically important imbalance between the treatment groups will be noted.

5 Analysis

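### Two subgroups in SAP 5.3.7 are defined after inclusion: the mask-use interaction cannot be estimated, and the cardioversion/antiarrhythmic strata are open to bias

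*SAP*

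**What the plan says.** SAP 5.3.7 lists seven subgroups for the primary outcome and six secondary outcomes. All seven are to be "analysed by adding a subgroup indicator variable and an interaction term between the subgroup and treatment to the linear regression model". A subgroup effect is declared when the interaction reaches the 5% level, and effects within and between subgroups are reported with 95% confidence intervals.

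Two of the seven rows are not baseline characteristics:

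- **Mask use.** The row is "Patients that use the CPAP mask for more than 4 hours a night vs. patients that use the CPAP mask" for under 4 hours, with the note "no change in the usual care group".
- **Cardioversion or drug start.** The row is "Patients who either have a DC cardioversion or start treatment of Flecainide, Dronedaron, or Amiodarone after inclusion", against patients with none of these.

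Neither row has its own model or a caveat. SAP 2.4.1 limits the weight of all subgroup results: "All other efficacy analyses will be regarded as supportive or exploratory".

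**The concern.** An interaction test asks whether the randomised treatment effect differs between two kinds of patient. Both kinds must exist in both arms, and membership should not depend on treatment.

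The mask-use row fails the first condition. Controls have no CPAP, so they cannot be split. Use in the run-in cannot supply the split either. The protocol's tolerability test sets this standard for entry: "Compliance is defined as > 4 hours per night every night for 7 nights". Everyone randomised should therefore be on the same side of 4 hours.

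The cardioversion/drug row fails the second condition. Randomisation comes one month after loop-recorder implantation (SAP 2.2), followed by five months of open-label treatment. Most qualifying events can therefore occur after allocation is known. If AF burden prompts these treatments and CPAP lowers burden, fewer CPAP patients enter the event stratum, and the arms within each stratum are no longer comparable.

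At stake is a published subgroup statement, for example that CPAP works in those who use it, that rests on self-selection.

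**Working it through.** **Scale.** SAP 2.3 takes a 25% reduction on a mean of 34%, which is 0.25 × 34 = 8.5 points, with SD 12. A two-sample t-test calculation at 80% power and two-sided 5% gives 32.3, so 33 per group, as stated. With SD 15 it gives 49.9, so 50 per group, or 100 in total, also as stated. Biases below can be read against 8.5 points.

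**Mask-use row: can the model be fitted?** Let T be treatment, S the subgroup indicator, and add site and baseline burden as in SAP 5.3.1:

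Y = b0 + b1·T + b2·site + b3·baseline + b4·S + b5·S×T

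Write C, L and H for the adjusted means of controls, CPAP under 4 h and CPAP over 4 h.

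- Controls coded S = 0: S×T = S in every patient. C = b0, L = b0 + b1, H = b0 + b1 + b4 + b5. Only the sum b4 + b5 is identified.
- Controls coded S = 1: S×T = S + T − 1 in every patient. C = b0 + b4, L = b0 + b1, H = b0 + b1 + b4 + b5. Four coefficients rest on three means.

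A numerical check with 50 patients per arm gives rank 5 for 6 columns under both codings. If software drops a column, the result depends on the choice. With controls coded 0, the surviving coefficient is H − L. With controls coded 1, the interaction coefficient is H − L if S is dropped, but H − C if T is dropped.

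**Mask-use row: size of the false signal.** Assume no CPAP effect, 50 per arm, residual SD 12, a share p of the CPAP arm above 4 h, and correlation r between adherence and prognosis. With a normal latent adherence trait cut at z, the expected false benefit is:

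- H − C: 12 × r × φ(z)/p
- H − L: 12 × r × φ(z)/[p(1 − p)]

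Example, p = 0.7 and r = 0.3: φ(z) = 0.348. H − C is 12 × 0.3 × 0.348/0.7 = 1.8. H − L is 12 × 0.3 × 0.348/0.21 = 6.0. Simulation (8,000 trials per cell) agrees closely:

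| Contrast | p | False benefit, points (r = 0.2/0.3/0.5) | False positives (r = 0.2/0.3/0.5) |
|---|---|---|---|
| H − C | 50% | 1.9 / 2.9 / 4.8 | 10 / 16 / 36% |
| H − C | 70% | 1.1 / 1.8 / 3.0 | 7 / 10 / 20% |
| H − C | 80% | 0.8 / 1.3 / 2.1 | 6 / 8 / 13% |
| H − L | 50% | 3.8 / 5.7 / 9.5 | 19 / 38 / 82% |
| H − L | 70% | 3.9 / 5.9 / 9.9 | 17 / 34 / 79% |

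At r = 0 both contrasts reject in about 5% of trials. The documents give neither p nor r. The run-in makes p above 50% plausible.

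**Mask-use row: copying all controls into both strata.** This makes the model fit, with 150 rows from 100 patients, but ordinary standard errors are then wrong. When use is unrelated to prognosis, the mean model standard error is 3.67 against an empirical 3.11, and the test rejects in 2.3% of trials at nominal 5%. With no CPAP effect, 60% above 4 h and a 3-point burden shift per SD of the latent trait (both assumed), the strata show +2.8 (under 4 h) and −2.0 (over 4 h), and the test rejects in 21% of trials.

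**Cardioversion/drug row.** Assume a uniform true effect of −8.5 points. Starts are triggered by early burden in 30–50% of controls (11–24% of CPAP patients), with early-late correlation 0.5–0.8. Fitting the SAP 5.3.7 model (6,000 trials per setting):

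- Starters: −4.0 to −5.9 points.
- Non-starters: −5.2 to −7.0 points.
- Interaction test: rejects in 4–5% of trials.

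A separate model, with event probability rising with on-study burden (28% of controls, 12% of CPAP), gives −4.6 with an event and −6.4 without. With no CPAP effect and a trigger that depends on burden alone, there is no bias. If open-label care alone makes starts differ (28% against 20%), spurious effects of +1.9 (event) and +1.1 (no event) appear.

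**The case against.** The best defence of the mask-use row is that its note shows the authors foresaw an undivided control arm and meant it as a common comparator. With controls coded 0, one column is merely redundant, and the remaining coefficient equals (H − C) − (L − C). The request for effects within and between subgroups would then ask for H − C, L − C and H − L, all available from one three-group model. This is a fair reading, but it does not rescue the test. Controls cancel, since (H − C) − (L − C) = H − L, so the 5% rule would be applied to a comparison of self-selected groups within one arm.

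The point biases may also be at the upper end. SD 12 is given for AF burden itself, while the model adjusts for baseline. With an assumed baseline-outcome correlation of 0.5 or 0.7 the residual SD shrinks by √(1 − 0.25) = 0.87 or √(1 − 0.49) = 0.71, so 4.8 points becomes about 4.2 or 3.4. Rejection rates at a given residual correlation do not change. This stands, and the figures are illustrative.

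For the cardioversion/drug row, the interaction test held its nominal level in the simulation, and the within-stratum effects might be reported only after a significant interaction. That stands as far as it goes. The problem lies in the within-stratum estimates, and a test at its nominal level does not give those strata a causal reading.

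Finally, these are two rows of a supportive or exploratory analysis. That limits the severity, but it does not make an unidentified term estimable.

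**Conclusion.** The concern holds. The mask-use result is algebra. It needs only that usual care is left undivided, which the SAP states, and it applies to all seven outcomes in SAP 5.3.7. The analyst would have to settle on a replacement model at the analysis stage, and the available contrasts can present a healthy-adherer difference as a CPAP effect. How large that difference is depends on an unknown adherence share and an assumed correlation. Plausible settings run from negligible (0.8 points, 6% false positives) to larger than the 8.5-point target (9.9 points, 79%).

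The cardioversion/drug row can be fitted, and its bias is conditional. It arises if CPAP, or knowledge of allocation, changes who is cardioverted or started on a drug, and not otherwise. Under the burden-triggered scenarios both strata understate a real effect.

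The primary analysis and the sample size are untouched. This should be corrected, but it does not threaten the main result.

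**What to change.** In SAP 5.3.7:

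1. Limit the interaction model and the 5% rule to subgroups defined at baseline: sex, age, AF duration, left atrial size and BMI, each at its baseline value.
2. Move mask use to a descriptive summary within the CPAP arm, labelled non-randomised. SAP 3.2.1 already commits to the count: "The number and % of participants using the CPAP device more than four hours per night will be presented". State the averaging period, which 5.3.7 omits (3.2.1 uses the last three months), and assign exactly 4 hours to a group.
3. Report cardioversions and antiarrhythmic starts by arm. If outcome is also shown by these events, label it descriptive and non-randomised.

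This changes wording only and needs no new data. The cost is the loss of a formal test for two rows: one cannot be estimated as written, and the other has no clear causal meaning. An instrumental-variable analysis of CPAP use, or extra baseline subgroups for previous cardioversion or drug use, could be added but is not needed to cure the defect.

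### SAP 5.3.7 declares a subgroup effect from any of up to 42 interaction tests at an unadjusted 5%, so at least one false declaration is likely even if CPAP acts identically in everyone

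*SAP*

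**What the plan says.** SAP 5.3.7 takes the primary outcome and six secondary outcomes (numbers 8, 9, 11, 12, 13 and 14 in the table of SAP 5.1.4) into subgroup analysis. It lists seven factors: sex, age, duration of AF, left atrial size, BMI, nightly CPAP mask use, and cardioversion or start of an antiarrhythmic drug after inclusion. Four are cut at the median, for example "Duration of AF below median vs. duration of AF above median". For mask use, a bracket adds "no change in the usual care group", so the usual care arm is not divided.

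Each comparison adds a subgroup indicator and its product with treatment to the regression model. The decision rule is: "A significant subgroup effect will be declared if the interaction term is statistically significant at the 5% level". The next sentence reads: "Within- and between subgroup effects will then be reported with mean differences and 95% confidence intervals". The section gives no adjustment for the number of tests, no ranking of the factors and no limit on interpretation.

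SAP 2.4.1 names a single primary analysis and adds: "All other efficacy analyses will be regarded as supportive or exploratory".

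**The concern.** The rule instructs the analyst to declare a finding whenever one of several dozen tests crosses 5%. With that many tests, some are expected to cross by chance. The plan would then have authorised in advance a statement that CPAP works better in some type of patient when it does not.

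The sentence that follows makes this harder to judge. The word *then* may mean that estimates are shown only after a significant interaction. Read that way, a declared subgroup would appear without the non-significant contrasts that put it in context.

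**Working it through.** **1. The plan's own figure.** The only figure in SAP 5.3.7 is the 5% level per test. The plan states no overall error rate for the subgroup analyses, so there is none to reproduce.

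**2. Number of tests.** Outcomes: 1 primary + 6 secondary = 7. Factors: 7. Listed combinations: 7 × 7 = 49.

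**3. Which of these are interaction tests.** Let T be 1 for CPAP and 0 for usual care, and let G be 1 for a CPAP patient with mask use above 4 hours. Every control has G = 0, so G × T equals G for every patient. The two columns are identical and the interaction cannot be estimated. What remains is a non-randomised contrast within the CPAP arm. Without this factor there are 6 × 7 = 42 tests.

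The cardioversion or drug factor is defined by events after inclusion and may be affected by treatment. Without it, 5 × 7 = 35 tests remain, on sex, age, duration of AF, left atrial size and BMI. I take these five as fixed at baseline.

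**4. Expected false declarations if the CPAP effect is constant.** This is the number of tests × 0.05, whatever the correlation between tests:
- 42 × 0.05 = 2.1
- 35 × 0.05 = 1.75

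**5. Chance of at least one, tests independent.** This is 1 − 0.95^k:
- k = 42: 1 − 0.95^42 = 88.4%
- k = 35: 1 − 0.95^35 = 83.4%

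**6. Chance of at least one, outcomes correlated.** Correlation lowers this chance. The documents give no correlations, so they were assumed. The simulation used 100 patients (50 per arm), the SAP model with site and baseline value, normal residuals, a constant CPAP effect and 1,500 runs per setting. Also assumed were equal correlation between all outcomes, correlation of 0 to 0.3 between factors, 70% men, and 30% with the post-inclusion event, unaffected by treatment.

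| Assumed outcome correlation | 42 tests | 35 tests |
|---|---|---|
| 0 | 87.9% | 83.5% |
| 0.3 | 83.3% | 77.9% |
| 0.5 | 77.4% | 70.2% |
| 0.7 | 69.4% | 63.1% |
| 0.9 | 48.9% | 43.1% |
| 0.99 | 32.7% | 28.5% |

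The mean number of false positives among the 42 tests stayed between 2.04 and 2.20, in line with step 4. The simulation error is at most √(0.5 × 0.5 / 1500) = 1.3 percentage points.

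**7. A narrower rule.** With the primary outcome and the five baseline factors only, the unadjusted chance under independence is 1 − 0.95^5 = 22.6%. Holm starts at 0.05 / 5 = 0.01 for the smallest P-value and keeps the chance of any false declaration at or below 5%.

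**The case against.** The best defence is SAP 2.4.1. There is one primary analysis and everything else is exploratory, so a subgroup result is exploratory by the plan's own terms and the primary type I error is untouched. That stands. A reader might go further and say that 2.4.1 and 5.3.7 contradict each other. They do not: a significance rule can sit inside an exploratory analysis. There is a tension, because the label limits how a result is read but does not withdraw the instruction to declare it.

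A second defence is that the SAP's contents list a section 3.1 on confidence intervals and P-values, and its text was not available for this review. A general statement on multiplicity may stand there and should be checked. Even so, 5.3.7 sets its own 5% rule.

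Third, a reader might infer that non-significant contrasts will be hidden. The documents do not say so. The word *then* can equally mean that reporting follows model fitting, and the section does say that the outcomes will be analysed in all the listed subgroups. This is an ambiguity, not a stated plan to omit results.

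Fourth, a reader might object to the median splits of age, BMI and left atrial size and want continuous interactions instead. Splitting can lose power, but fixed splits avoid data-driven cut-points and do not assume a linear effect. The documents give no distributions on which to settle this, so it forms no part of the point.

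**Conclusion.** The point holds for the declaration rule. If CPAP acts identically in everyone, the rule is expected to produce about 2.1 false declarations from 42 interaction tests, or 1.75 from the 35 on baseline factors. At least one false declaration from 42 tests has a chance of 88% under independence and about 69% to 83% for assumed outcome correlations of 0.7 to 0.3. It drops to about half only near 0.9. I judge that implausible across device-measured AF burden, AFSS, SF-36, ESS and FOSQ.

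Two larger figures are tempting. Counting all 49 combinations gives 49 × 0.05 = 2.45 expected and 1 − 0.95^49 = 92%, but this includes seven interactions that cannot be estimated. Quoting 88% alone treats the independence case as the answer, although seven outcomes on the same patients are unlikely to be independent.

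The result rests on each test having a true 5% error rate. The post-inclusion factor may not meet that, because treatment may influence it. A switch to median regression under SAP 5.3.4 would not change the number of tests. What is at stake is over-interpretation of subgroups. The primary conclusion is not at risk.

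**What to change.** Delete the declaration sentence in SAP 5.3.7 and replace it, with the sentence after it, by wording such as:

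*Interaction estimates with 95% confidence intervals will be reported in a forest plot for each of the five baseline factors and each of the seven outcomes (35 estimates), whatever their P-values. These analyses are exploratory, the number of tests will be stated, and no subgroup effect will be declared.*

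In addition:
- If a declaration is wanted, restrict it to the primary outcome and the five baseline factors, with a Holm correction over the five tests.
- Take the mask-use split out of the interaction model and report it descriptively.
- Present the cardioversion or antiarrhythmic drug factor separately, flagged as arising after inclusion and possibly affected by treatment.
- State that the five remaining factors are taken at baseline.

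This costs a change of SAP wording and one figure, with no new data. The downside is that the trial gives up subgroup claims at a nominal 5%.
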